VERSION DATE: 9/8/21

STUDY TITLE:

Trans-abdominal fetal pulse oximetry: PILOT 1

STUDY SPONSOR:

Raydiant Oximetry, Inc. [name]

Version No.	Version Date	Modifications
V1	3/15/21	N/A- Original Release
V2	4/9/21	Added exclusion criteria to correspond
		with Nellcor IFU
V3	6/7/21	Clarification of inclusion induction/active
		labor enrollment, timing& removal device,
		Amazon card replaced with UTMB
		Clincard, defined health provider
		(physician, midwife, nurse practitioner,
		nurse)
V4	7/14/21	Additional clarifications added in the
		Background, Procedures, and Risks
		Sections.
		Added that internal sensor previously
		manufactured by Nellcor, is now
		manufactured by Axcesor. Clarification on
		enrollment and sensor comparison
		statistics.
V5	9/8/21	Remove reference to sterile sleeve, replace
		words to indicate internal sensor is
		sterilized.

VERSION DATE: 9/8/21

Study Synopsis

Title: Trans-abdominal fetal pulse oximetry; PILOT 1

Study Design: Prospective, observational, investigator-blinded study.

Study Device: The Raydiant Oximetry Sensing System (LUMERAH)

Objectives: 1) Assess safety and performance of the LUMERAH device as an adjunct to cardiotocography; 2) Assess human factors, device usability factors, and signal capture; and 3) Compare device output to "ground truth" technology (Nellcor N-400 with internal sensors manufactured by Axcesor).

Safety Endpoints

Rate of device-related adverse events such as erythema or rash on the maternal abdomen at the location of the sensor. Note: In this study, use of the device provides additional clinical information, but clinical judgement is based on standard fetal monitoring, including cardiotocography, and investigators are blinded to oximetry readings. The maternal skin at the sensor site will be examined intra and postpartum.

Effectiveness Endpoints

Primary efficacy endpoint is concurrence of oximetry readings compared to those of the Nellcor N400 System ("ground truth").

Study Populations:

Up to 60 pregnant women. who are/have:

- 1) Willing and capable to provide informed consent
- 2) Age \geq 18 years
- 3) BMI < 50 (with no more than 4 cm between maternal skin and fetal skin)
- 4) Gestational age > 36 weeks
- 5) Singleton pregnancy
- 6) Vertex presentation
- 7) Active labor
- 8) Category I or Category II tracings
- 9) Ruptured amniotic sac with cervical dilation of ≥ 2 cm and a station of -2 or lower

Exclusion Criteria

- 1) Age < 18 years

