This is a prospective, observational, investigator-blinded study. One to two sites in the United States will participate in this study. IRB approval will be obtained prior to entering data in the screening and enrollment logs. The Principal Investigator or research team member may consult a list of eligible patients based on predicted delivery dates and scheduled inductions. Women who are planning to undergo labor

VERSION DATE: 9/8/21

will be approached regarding this study. The enrollment log will be a separate log which will contain the key linking subject information with the study ID. Study ID will be assigned to subjects in a sequential order (e.g., 01-001, 01-002, 01-003....). Subject initials will not be included in the study ID. Logs will be stored on password protected desktops of the study team in a research folder accessible to the OBGYN/Pediatric study team only. The infants born of the subjects will be identified with an "n" following the subject number (e.g., 01-001n).

During this study, women will also undergo sonographic evaluation to assess distance from maternal skin to fetal tissue and to confirm fetal presentation and position. Although sonography is performed routinely during pregnancy, these measurements and confirmation at or after 36 weeks is not routine. The internal sensor (manufactured by Axcesor) will be placed according to the Instructions for Use but only after membranes are ruptured. The LUMERAH device will be simultaneously positioned on the maternal abdomen in various locations depending on the sonographic evaluation. The LUMERAH sensor will obtain fetal pulse oximetry signals for a period of at least 10 minutes but no greater than 6 hours during active labor.

PROCEDURE / TEST	Pre- partum	Peri- Partum
Subject Medical / Clinical History	$\sqrt{}$	
Subject Informed Consent	$\sqrt{}$	
General Inclusion / Exclusion Criteria	$\sqrt{}$	
LUMERAH external and Nellcor/Axcesor internal		√ √
data collection		,
Adverse Events (AEs)		$\sqrt{}$

The Sponsor anticipates that this study will require about 6 months to enroll up to 60 subjects and another month to complete the primary analyses.

4. Enrollment Criteria:

This study will **include** pregnant and laboring women who are:

- 1) Willing and capable to provide informed consent
- 2) Age > 18 years
- 3) BMI < 50 (with no more than 4 cm between maternal skin and fetal skin)
- 4) Gestational age > 36 weeks
- 5) Singleton pregnancy
- 6) Vertex presentation
- 7) Active labor

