Subjects will be consented upon admission to the labor and delivery unit in a private setting. Upon admission to labor and delivery, information will be delivered orally and in writing. If a patient agrees to participate at this time, consent will be obtained. It is assumed that at least 50% additional subjects (for a total of up to 90 subjects) will be initially consented compared to the number actually completing the study due to the inclusion/exclusion criteria that cannot be fully ascertained upon admission. In addition, a subject may originally consent to the study but change her mind once labor begins. The *i*nformed consent process will not be rushed and subjects will be informed that their participation is voluntary and there will be no change in their medical care if they choose not to participate. Investigators will describe the safe, noninvasive nature of this study, as well as the future benefit to women and their fetuses if measurement of fetal oxygenation can be performed. Subjects will be invited to ask questions, provide comments, or can choose to withdraw from participation at any time. A copy of the signed Informed Consent Form will be provided to each subject who chooses to participate.

Subjects who agree to participate and who complete participation (defined as device placement and monitoring) will receive a \$150 UTMB Clincard.

7. Duration of Subject Participation

Following consent and baseline data collection, subjects are expected to actively participate in the study for up 6 hours (active labor stage). Subjects end their participation in the study after that time period.

VERSION DATE: 9/8/21

8. Payment to Subjects/Cost of Participation

There is no expected cost of subject participation. Payment to the subjects who choose to participate will be set according to institutional standards.

9. Study Procedures/Device Use

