De-identified sonographic pictures will be obtained by a trained healthcare provider (physician, midwife, nurse practitioner, nurse) from the site for each test location of the optical sensor. The de-identified image will be uploaded to the database which is a secure web application for building and managing online surveys and databases. The study team will take every precaution to ensure that the image is completely free of identifiers.

A single de-identified photograph showing the position of the sensor for each test location on the maternal abdomen may be obtained on a stylized image. This image will be uploaded to the database which is a secure web application for building and managing online surveys and databases. The study team will take every precaution to ensure that the image does not capture any identifiable portion of the patient. All data will be de-identified prior to data entry in the database.

To verify accuracy of the LUMERAH algorithm for laboring women, as derived from experimental studies in the pregnant ovine model, Raydiant Oximetry will use a Nellcor N-400 system with a sterile internal sensor (manufactured by Axcesor) in all subjects. The internal sensor will be placed *after* rupture of membranes (amniotic sac) and the fetus has descended to at least a -2 station. The sensor will be placed by a trained healthcare provider (physician, midwife, nurse practitioner, nurse) and the placement confirmed before initiation of LUMERAH data collection. The data collection plan is to obtain approximately 40 data sets on each of the laboring patients. Each data set takes 90-120 seconds to gather (~ 2-3 hours in total), and a pre/post ground truth assessment will be obtained for each data set. It is anticipated that subjects will participate for a minimum of 10 minutes (where only a few data sets are obtained) but for no more than 6 hours. The obstetric provider will be blinded to both the LUMERAH data and the internal sensor data.

VERSION DATE: 9/8/21

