The device shipments/delivery and request for return will be the responsibility of the Sponsor. The device is not delivered to the site until IRB approval has been obtained. The Investigational device is precommercialization and will not be available to study subjects after participation in the study. Study subjects will not be restricted from use of any medication or other substance while participating in the study. In addition to the PI and co-investigators, members of the Raydiant Oximetry team may transport and be accountable for the investigational device.

10. Data Collection

In addition to specific LUMERAH device and cardiotocography data, the following data is the minimum subject data set to be collected during this study:

- Maternal demographics such as race, ethnicity, age, parity, prior perinatal outcomes, height, weight (to calculate BMI), number and date of prior cesarean deliveries, Maternal Vital Signs such as the maternal heart rate and maternal oxygen saturation.
- CTG Tracings to be downloaded from the EMR
- Location on maternal abdomen for best signal quality
- Safety data (see "Adverse Event Reporting" below)

In addition, the internal sensor data will be analyzed and compared to the LUMERAH device data. We will report the mean error, standard deviation of difference and root-mean square error from the study results. In addition, we will present a scatter plot (with the identity line and Deming regression line), a Bland-Altman plot [with the 95% limits of agreement (LoA)] and report the repeatability and reproducibility by providing a population mean bias (μ 0), between-subject variance (σ 2) with our final statistical analyses.

Neonatal outcomes will not be collected during this study.

11. Risks to Subjects/NSR Determination

A significant-risk (SR) device study is defined by the United States Food and Drug Administration (https://www.fda.gov/media/75459/download) as one that:

- Is intended as an implant and presents a potential for serious risk to the health, safety, or welfare of a subject;
- Is purported or represented to be for use supporting or sustaining human life and presents a potential for serious risk to the health, safety, or welfare of a subject;
- Is for a use of substantial importance in diagnosing, curing, mitigating, or treating disease, or otherwise preventing impairment of human health and presents a potential for serious risk to the health, safety, or welfare of a subject;

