Subjects may experience some minor inconveniences and discomfort associated with using the internal sensor (now manufactured by Axcesor) but there are no foreseeable medical risks, discomforts, or hazards associated with its use other than the potential for infection. To mitigate this risk, the Sponsor has planned to use a newly manufactured, sterile internal sensor. Due to the placement of the internal sensor on the cheek of the fetus, it is possible that the baby has a noticeable red mark or bruise on the cheek after birth. The LUMERAH device may cause a temporary warmth and redness on the abdomen where the sensor is placed. Although unlikely, women with extremely sensitive skin could potentially develop a rash at the location of the sensor. There is a small risk of unintentional loss of confidentiality. All efforts will be made to minimize this risk. There are no anticipated emotional, psychological, economic, legal, or social risks to the subjects associated with this study.

12. Potential Benefits to Subjects

There is no direct potential benefit to subjects. However, the study results may provide data necessary to refine the plans for future studies and device development, satisfy the requirements imposed by the U.S. Food and Drug Administration, and provide "ground truth" knowledge of the LUMERAH device. Overall, this study may lead to greater diagnostic capability during gestation to diagnose intrapartum fetal hypoxia and monitor fetal well-being that would benefit the population from which the subjects are recruited, benefit science and humanity in general.

13. Alternatives to Participation

Subjects will receive the standard care per clinical indication regardless of participation in the study. Declining to participate will not affect their clinical care. This is an observational study only, with no impact on standard care. This research device testing will be conducted only in a clinical research setting.

VERSION DATE: 9/8/21

14. Confidentiality

The principal risk of a signed consent document would be the potential harm resulting from a breach of confidentiality. Every precaution will be taken to minimize this. The original signed consent documents will be stored in the research office which will be locked when not attended. Electronic logs will be stored in password protected desktop computers, accessible only to the research team. Data will be stored for 7 years after study is closed out with the IRB office(s).

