At any given time, there will be 1 to 3 people from the Sponsor and/or site's research team present to abstract data with the Investigational device. De-identified data will be collected in the database which will be accessible to outside institution team members. Data transferred out of the site will be de-identified data with the study ID number. The key containing the study ID number with the subject information will be accessible to the study team only and will be stored securely on password protected computers. No genetic information will be collected for this study.

15. Adverse Event Reporting

An adverse event (AE) is any untoward medical occurrence in a patient or clinical study participant, temporally associated with the use of study treatment, whether considered related or not related to the study treatment.

A serious adverse event (SAE) is any untoward medical occurrence that:

- Results in death
- Is life-threatening
- Requires subject hospitalization or prolongs the post treatment hospitalization
- Results in persistent or significant disability or incapacity
- Causes a congenital anomaly in the offspring of the subject, or
- Is considered an important medical event that jeopardizes the health of the subject or requires surgical intervention to prevent one of the outcomes listed above.

No adverse or serious adverse events are anticipated as this study poses no additional known risks to subjects. Nevertheless, any serious adverse events associated with use of the Investigational device will be submitted to the IRB in writing within 24 hours of learning about the SAE. Reportable new information will be reported to the IRB per the institutional policy.

16. Statistical Considerations

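### The plan foresees a cheek mark on the newborn from the internal sensor but schedules no look for it, so no rate can be reported for up to 60 exposed infants

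*Combined protocol and SAP*

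**What the plan says.** All references are to the combined protocol and SAP.

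- **Exposure.** Section 9 uses the Nellcor N-400 "with a sterile internal sensor (manufactured by Axcesor) in all subjects". Every fetus that is monitored is therefore exposed.
- **Foreseen effect.** Section 11 notes that the sensor sits on the fetal cheek and says "it is possible that the baby has a noticeable red mark or bruise on the cheek after birth".
- **Data rule.** Section 10 ends with "Neonatal outcomes will not be collected during this study". Its minimum data set does include safety data, by reference to Section 15, but it lists no infant variable.
- **Infant identifiers.** Section 3 provides for them: "The infants born of the subjects will be identified with an" n after the subject number.
- **Adverse events.** Section 15 defines an adverse event as one occurring in a patient or study participant, and does not say whether the newborn is included. It also states: "No adverse or serious adverse events are anticipated as this study poses no additional known risks to subjects".
- **Safety endpoint.** The synopsis endpoint is a rate of device-related adverse events, with maternal abdominal skin reactions as the examples. It adds: "The maternal skin at the sensor site will be examined intra and postpartum". It gives no matching sentence for the newborn.

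**The concern.** The sponsor names one visible effect on the newborn, exposes every fetus to its possible cause, and plans no observation of it. The internal sensor is newly manufactured, and it is placed only for research, since its readings do not guide care.

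Without a planned look at each infant, an absence of reports cannot be told apart from an absence of marks. The study could finish with some scattered reports or none, and neither result would support a statement about how often the sensor leaves a mark. The Section 15 sentence that no adverse events are anticipated adds to this. It does not fit the effects that Section 11 names, and it gives staff no prompt to record a cheek mark.

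**Working it through.** No figure in the plan is in dispute, so there is nothing to reproduce. The check sets the sections side by side and then asks what a single inspection would give.

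**Step 1: is a cheek assessment planned anywhere?**

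| Place | What it contributes | Does it plan a look at the cheek? |
|---|---|---|
| Synopsis, Safety Endpoints | Maternal skin examination | No |
| Section 3, schedule | Five rows: history, consent, eligibility, device data, adverse events | No |
| Section 3, text | Infant study IDs | No; an ID without a listed variable |
| Section 10 | Safety data by reference; neonatal outcomes excluded | No |
| Section 11 | Names the mark as possible | No |
| Section 15 | General adverse-event definition; 24-hour IRB reporting of serious events associated with the investigational device | No; a red mark would not normally be serious |

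Planned newborn cheek assessments: 0 of up to 60.

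**Step 2: what would one look per infant give?**

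Inputs: n = 60 (maximum enrolment, Sections 3 and 16), n = 48 (calculated sample size, Section 16) and n = 30 (stated minimum for the device comparison, Section 16). The documents give no cheek-mark rate, so the true rates below are assumptions.

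With zero events, the upper end of the two-sided exact (Clopper-Pearson) 95% interval is 1 − 0.025^(1/n):

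- n = 60: 1 − 0.025^(1/60) = 0.0596, interval 0 to 6.0%
- n = 48: 1 − 0.025^(1/48) = 0.0740, interval 0 to 7.4%
- n = 30: 1 − 0.025^(1/30) = 0.1157, interval 0 to 11.6%

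With events observed, the same method gives 1.7% (0.04% to 8.9%) for 1/60 and 5.0% (1.0% to 13.9%) for 3/60.

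The chance of seeing at least one mark is 1 − (1 − p)^n:

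| Assumed true rate p | n = 30 | n = 60 |
|---|---|---|
| 1% | 26% | 45% |
| 2% | 45% | 70% |
| 5% | 79% | 95% |
| 10% | 96% | 99.8% |

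Sixty inspections would very probably show a mark that occurs in 5% or more of infants, and would put a useful upper limit on the rate if none were seen. As written, the plan supports neither statement.

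**The case against.** The strongest reply is that the Section 10 sentence means clinical outcomes. The protocol's neonatal concern throughout is metabolic acidosis and hypoxic injury, and the same section lists safety data. On that reading a device-related mark remains reportable: infants have IDs, the adverse-event definition is broad, and the synopsis endpoint gives maternal skin reactions only as examples. This stands in part. A reader might infer that the plan forbids recording any newborn event, and the documents do not support that. But the sentence carries no such limit, and even on the generous reading nobody is assigned to look, so there is still no denominator.

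A second reply is that the consequence is small. No endpoint, analysis or sample size rests on cheek marks. Section 11 foresees no medical risk from the sensor other than infection, and Section 16 links PILOT 2 to collecting ground-truth cases, not to a safety threshold. All of this is correct and limits the weight of the point. The intervals above show what an inspection would give; they do not measure harm.

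Third, the consent form pages were removed from the text reviewed and no case report form is included. Either might describe newborn event capture. That cannot be settled here.

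A reader might also infer that the maternal skin examination is missing, because Section 7 says "Subjects end their participation in the study after that time period" and the schedule has no postpartum column. The documents do not support that. The synopsis plans the examination, Section 6 treats participation as "complete participation (defined as device placement and monitoring", and the schedule is a summary that also leaves out the sonography that is plainly planned. Adding the examination to the schedule would be an editorial tidy-up.

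**Conclusion.** The point holds for the newborn. A foreseen effect of a research-only sensor has no scheduled assessment, and the adverse-event scope for newborns is unstated. As written, no rate can be given for up to 60 exposed infants, whatever the true rate. One look at each of 60 would give an interval of 0 to 6.0% if no mark were found.

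This rests on the protocol text alone, on one exposed newborn per subject (singletons only), and on all 60 being enrolled and examined.

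A reader might go further and infer that the LUMERAH safety rate is biased. It is not: that endpoint's examples concern maternal skin under a different sensor. The gap is in safety information on the internal sensor. It is modest in consequence and worth closing because doing so costs little.

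**What to change.** 1. **Section 10.** Reword the sentence so that neonatal clinical outcomes, such as acid-base status, are not collected, but device-related newborn findings are.
2. **Data item.** Abstract presence or absence of a cheek mark or bruise from the routine newborn examination before discharge, under the existing infant IDs. Record whether the examination result was available, so that the denominator is known.
3. **Section 15.** State that device-related newborn findings count as adverse events, and correct the sentence that none are anticipated so that it agrees with Section 11.
4. **Reporting.** Give internal-sensor events over newborns examined, with an exact 95% confidence interval, separately from LUMERAH events.

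The cost is one extra record field per infant and matching consent wording. Sensor time and sample size do not change.

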• Category I fetal heart rate tracings are considered normal and occur exclusively in about 15% of the all pregnancies in the United States. 11 When the clinician identifies Category I, no intervention is needed to address concern to the fetus. Category I FHR tracings are *normal*. Category I FHR

tracings are strongly predictive of normal fetal acid-base at the time of observation and may be followed in a routine manner with no specific action required.

- Category III fetal heart rate tracings are considered ominous and occur in less than 5% of pregnancies in the United States. ¹² Category III fetal heart rate tracings typically require immediate intervention to protect the fetus. The National Institute of Child Health and Human Development (NICHD) states, "Category III FHR tracings are *abnormal*. Category III tracings are predictive of abnormal fetal acid-base status at the time of observation. Category III FHR tracings require prompt evaluation. Depending on the clinical situation, efforts to expeditiously resolve the abnormal FHR patter may include, but are not limited to, provision of maternal oxygen, change in maternal position, discontinuation of labor stimulation, and treatment of maternal hypotension." ¹³ In this study, Category III tracings are excluded.
 - Category II fetal heart rate tracings are considered indeterminate and occur in about 80% of pregnancies in the United States. ¹⁴ However, it is often challenging for obstetric clinicians to determine whether a Category II fetal heart rate tracing truly represents a situation of concern to the fetus and consequently has resulted in the overuse of intervention, including a high rate of medically unnecessary cesarean delivery. ¹⁴ Application of the standard algorithm may be initially delayed for up to 30 minutes while attempts are made to alleviate category II pattern with conservative therapeutic interventions (e.g., correction of hypotension, position change, amnioinfusion, tocolysis, reduction or discontinuation of oxytocin). It has been well demonstrated that Category II CTG tracings have poor agreement with newborn metabolic acidosis ¹⁵. This is the target population for this study.

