In the case of Category II heart tracings, which represent the majority (80%) of all fetal heart rate tracings during labor, as indicated above, standard care CTG technology, even under ideal circumstances, has been demonstrated to have poor ability to identify infants born with metabolic acidosis ¹⁶. CTG further exhibited a staggering 99% false positive rate for prediction of cerebral palsy, a severe potential consequence of fetal hypoxia that remains untreated. ¹⁷ Further, CTG has been and prior studies reported as high as 89% false positive rate for predicting newborn metabolic acidosis. ¹⁸ Umstad et al. reported that fetal heart rate monitoring has a 6.2% positive predictive value and 24.1% sensitivity for detecting newborn metabolic acidosis (defined by a pH <7.12). ¹⁹

In addition to the widely-used CTG, there are a few alternative technologies for assessment of the fetus at risk for metabolic acidosis, such as analyses of the ST segment of the fetal electrocardiogram, fetal scalp stimulation and fetal scalp blood sampling for lactate and/or pH determination. However, overall these ancillary tests have not proved reliable. Fetal scalp sampling is invasive, requires transvaginal placement of a probe or similar tool to access the fetal scalp, and once accessed, the device penetrates the fetal scalp and is thus associated with risks such as bleeding and infection. It may require repeating. All the while, none of these technologies directly assess fetal oxygen saturation.

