This is an observational, noninvasive study with primary endpoints related to the LUMERAH device correlation with the Nellcor device and internal sensor (manufactured by Axcesor). Raydiant Oximetry met with the FDA on Feb 11, 2020 and suggested that we power our pilot and pivotal studies for specificity, and not sensitivity, because poor specificity of CTG technology is the unmet clinical need in obstetrics. CTG technology has a 29% specificity and the FDA agreed with this approach. Seelbach-Gobel²³ demonstrated that the Nellcor fetal pulse oximetry device had a specificity of 65% for the detection of newborn metabolic acidosis. The incidence of newborn metabolic acidosis has been reported to be 2-4% and the incidence of hypoxic fetuses is 3-4%. Our sample size calculations are based on a significance level of 0.05 (i.e. type 1 error=0.05) with the goal to achieve power of 0.8 and a lower confidence level of 80% to establish a clinical proof of concept. The sample size calculation, under these assumptions, is 48 subjects for this pilot study.

VERSION DATE: 9/8/21

To compare the Nellcor N-400 device output to the LUMERAH output, we are following the FDA guidance document (dated March 4, 2013) for pulse oximeters, where the in-vivo validation set should include at least 200 data points from 10 or more human subjects. Per the FDA recommendation, we will report the root mean square (RMS) error and produce a scatter plot with the identity line and a Deming regression line. In addition, we will report a Bland-Altman plot with the 95% limits of agreement as well as the 95% confidence intervals for the limits of agreement.

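### Section 16 claims that 48 subjects give 0.8 power for specificity against a 29% CTG benchmark, but the study neither measures nor analyses that specificity, and 29% is not reconciled with the CTG figures in Section 1

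*Combined protocol and SAP*

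**What the plan says.** Section 16 reports that the pilot and pivotal studies were proposed to be powered for specificity, because poor CTG specificity is the clinical need. It gives two figures: "CTG technology has a 29% specificity and the FDA agreed with this approach", and, from an earlier study, "the Nellcor fetal pulse oximetry device had a specificity of 65% for the detection of newborn metabolic acidosis". It adds an incidence: "The incidence of newborn metabolic acidosis has been reported to be 2-4" per cent. The calculation uses a "significance level of 0.05 (i.e. type 1 error=0.05) with the goal to achieve power of 0.8", plus a lower confidence level of 80% whose role is not explained, and ends at 48 subjects.

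The same section then gives a second rationale, for agreement with the N-400: at least 200 data points from 10 or more subjects, about 20 subjects for algorithm training and 10 for validation (minimum 30), and up to 60 so that about two hypoxic fetuses are seen.

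The Synopsis puts the first objective as "Assess safety and performance of the LUMERAH device as an adjunct to cardiotocography"; Section 2 words it as specificity in predicting newborn metabolic acidosis, as an adjunct to CTG. Section 10 lists "CTG Tracings to be downloaded from the EMR" among the data, and says that neonatal outcomes are not collected. Section 1 states that "fetal heart rate monitoring has a 6.2% positive predictive value and 24.1% sensitivity for detecting newborn metabolic acidosis" (pH <7.12), and also mentions a CTG false positive rate as high as 89%.

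**The concern.** A sample size with a stated power promises that a named test will be done and will have that chance of success. Here the implied test is oximetry at 65% specificity against CTG at 29%, for newborn acidosis. If the study collects no acidosis outcome and plans no such test, 48 and 0.8 describe a property it does not have.

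The benchmark matters as well. A device with 65% specificity beats CTG if CTG is 29%, and falls short of it if CTG is 85% or more. Section 16 links the specificity approach to both the pilot and the pivotal study, so an unreconciled figure could carry into pivotal planning.

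**Working it through.** **1. Reproducing 48.** Inputs from Section 16: p0 = 0.29, p1 = 0.65, alpha 0.05, power 0.80. Formula and sidedness are not stated. One-sided, two independent groups, pooled variance, no continuity correction, with mean proportion 0.47:

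n per group = [1.645·√(2·0.47·0.53) + 0.842·√(0.29·0.71 + 0.65·0.35)]² / 0.36² = 22.7, so 23 per group and 46 in total.

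Dividing 46 by 0.97 or 0.96 (3% or 4% affected) gives 47.4 or 47.9, so 48. Other standard versions miss:

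| Version | Total |
|---|---|
| Two groups, two-sided | 58 |
| Two groups, one-sided, continuity correction | 56 |
| Two groups, unpooled, one-sided / two-sided | 42 / 54 |
| One sample, exact, one-sided / two-sided | 14 / 18 |
| Paired (McNemar, independence assumed), one-sided / two-sided | 25 / 32 |

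The match is therefore inferred, after trying several versions. The version that fits assumes separate CTG and oximetry groups. In this study each woman has both.

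**2. Power as a single-arm test.** At 2% incidence, 48 × 0.98 = 47 women are unaffected. An exact one-sided test of 29% at 0.05 rejects at 20 or more negatives of 47 (size 0.033). With true specificity 65%, power is 0.9995. Against a null of 85% or more it is below 0.0001. Neither is 0.8.

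**3. Can the study do the test?** Specificity for newborn acidosis is the share of test-negatives among infants without acidosis. That status is a neonatal outcome, and Section 10 excludes collecting it. The analyses listed in Sections 10 and 16 are mean error, SD of differences, RMS error, Deming regression, Bland-Altman limits, and bias with between-subject variance. All compare LUMERAH with the internal sensor. No specificity, rule for a positive CTG, or CTG result appears.

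**4. Does 29% fit Section 1?** With sensitivity Se, predictive value PPV and incidence p:

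specificity = 1 − Se·p·(1 − PPV) / [PPV·(1 − p)], with Se = 0.241 and PPV = 0.062.

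| Incidence | Implied CTG specificity | Highest PPV possible if specificity is 29% |
|---|---|---|
| 2% | 92.6% | 2.8% |
| 3% | 88.7% | 4.2% |
| 4% | 84.8% | 5.5% |

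The last column is p / [p + 0.71·(1 − p)], which takes sensitivity as 100%; it stays below the stated 6.2%. To reach 29%, the odds of acidosis must be 0.71 / (0.241 × 0.938/0.062) = 0.195, an incidence of 16.3%. Without any incidence, 24.1% sensitivity with 29% specificity gives a positive likelihood ratio of 0.241/0.71 = 0.34, worse than chance. The two figures cannot plausibly describe one CTG rule in one population.

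**5. The 89% figure.** Read as 1 − specificity, it gives CTG 11%. Read as 1 − PPV, it gives about 66-96% (sensitivity 24.1-100%, incidence 2-4%). Section 1 does not say which is meant.

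**The case against.** The strongest reply is that this is a calibration pilot. Its primary efficacy endpoint is concurrence with the N-400, and enrolment is governed by training, validation and the wish to see hypoxic fetuses. That stands: replacing or deleting 29% changes neither the primary analysis nor the cap of 60. It is also why the specificity claim can be withdrawn without loss to the design.

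Four stronger readings are tempting and are not supported.

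- *That 29% is wrong or contradicted.* No other CTG specificity is printed. The 85-93% applies Section 16's incidence to a cohort whose own incidence is not given, which used pH <7.12 and, by its title, early-labour tracings. A looser rule for a positive CTG can have 29% specificity while a stricter one has 24.1% sensitivity. The 89% figure, read as an upper bound on 1 − specificity, is compatible with 29%.
- *That 29% has no source.* Citation markers were lost elsewhere in the extracted text and the visible reference list is incomplete, so this cannot be established.
- *That 48 is an arithmetic error.* It can be roughly recovered, as shown. The fault is that the calculation belongs to a different design.
- *That the collected tracings should supply a paired comparison by entry category.* Calling Category II positive would make CTG specificity mirror the recruitment mix, since Category II is the target population. The Section 1 share, "Category I fetal heart rate tracings are considered normal and occur exclusively in about 15% of the all pregnancies", concerns whole labours, not entry. Entry category can precede up to six hours of monitoring. LUMERAH has about 40 data sets per woman and no per-woman rule, and its algorithm would be trained against the same N-400 reference.

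Nor does the FDA sentence settle the matter: it most naturally records agreement with powering for specificity, not with 29% as a value.

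**Conclusion.** The stated power of 0.8 with 48 subjects for specificity is not a property of this study. That conclusion needs no assumption about CTG: the outcome is not collected and the test is not planned. The mismatch in the formula is secondary and rests on an inferred calculation.

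The benchmark point is conditional. At the plan's own 2-4% incidence, Section 1's predictive value and sensitivity imply a CTG specificity 56-64 points above 29%. A different positivity rule, population or acidosis definition could explain the gap, but none is given. Whether a 65%-specific device beats CTG therefore depends on which figure is used.

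A reader might infer that the agreement endpoint is compromised. It is not. The damage is confined to the specificity sizing and to what the adjunct-to-CTG objective can be taken to show.

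**What to change.** In Section 16:

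- Withdraw the statement that 48 subjects give 0.8 power for specificity, and with it the use of 29% against 65% as the basis for the pilot's size.
- Rest the sample size on the rationale already in that section: N-400 agreement, algorithm training and prospective validation, with a minimum of 30 and up to 60 subjects.
- State that this pilot does not estimate specificity for newborn metabolic acidosis and does not test superiority to CTG. The first objective in Section 2 needs the same qualification.
- Do not carry 29% into pivotal planning until it has been reconciled with the Section 1 figures under one stated rule for a positive CTG and one acidosis definition.

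Do not add a paired comparison based on entry category.

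The cost is a few sentences and the loss of the power claim. No subjects, procedures or data are added, and the primary agreement analysis and enrolment are unchanged.
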